Appendix A – Phone Survey 1 – week following dosage

NOTE: the following questions will be based on the previous week only and will be about how you usually feel or symptoms you otherwise usually have.

- 1) Over the last week, since you have taken the vitamin D3 of 250,000 IU have you:
 - i) Experienced feeling an increased amount of nausea?
 - (1) NO
 - (2) YES
 - ii) Experienced an increased frequency of emesis (vomiting)?
 - (1) NO
 - (2) YES
 - iii) Experienced an increased amount of diarrhea?
 - (1) NO
 - (2) YES
 - iv) Experienced any constipation?
 - (1) NO
 - (2) YES
 - v) Experienced increased gas production, such as burping or passing gas?
 - (1) NO
 - (2) YES
 - vi) Experienced an increased amount of abdominal pain/stomach aches?
 - (1) NO
 - (2) YES
- 2) Since taking the vitamin D3 last week, have you experienced an increase in heart burn or reflux?
 - i) NO
 - ii) YES
- 3) Did you find the one-time dose of vitamin D3 to be easy to take?
 - i) NO
 - ii) YES

Date: December 20, 2016

Principal Investigator: [name]

Application Number: IRB00081746 (IND # 128487 – IND Sponsor: [name])

- 4) Would this type of medication be something you would do next year if you had another low vitamin D level?
- i) NO
 - ii) YES
- 5) Would you prefer taking a one-time dose of vitamin D to treat a low vitamin D level instead of taking a daily vitamin D supplement?
- i) NO
 - ii) YES

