The following safety measures have been reviewed and approved by two Johns Hopkins All Children's Hospital Endocrinologists: As additional measures of safety at 7 days to the next working business day of the administration of the 250,000 IU of vitamin D3, all participants will also have a serum calcium and serum phosphorus level measured. If any participant has a serum calcium above the upper limits of normal (ULN) for their age (appendix B), they will be contacted via telephone to be queried about symptoms of hypercalcemia such as muscle weakness, confusion, vomiting, anorexia, confusion, polyuria and polydipsia. If the patient has more than 1 symptom of hypercalcemia and an elevated serum calcium level, we will consider this an adverse event. During this communication, it will be decided if any type of treatment will be needed to remedy the complaint (see section on treatment of hypervitaminosis D from hypercalcemia).

If any participant has a serum calcium level greater than the ULN for age or a serum phosphorus level greater than the ULN for age, a second tier of safety measures will be taken. This will include measuring a PTH with reflex calcium level as soon as possible, within approximately 7 days (± 3 days) of the serum calcium or phosphorus lab draw. In addition, we will obtain a spot urine calcium to creatinine ratio. Calcium levels and/or phosphorus levels will be repeated every 2 weeks (+7 days) until normalized for age. If the spot urine calcium to creatinine ratio is $> ULN$ for age (Appendix C) we will obtain an Endocrinology consult and if symptomatic be instructed to go to the Johns Hopkins All Children's Hospital for evaluation. The urine calcium to creatinine ratio will be repeated in 1 week (+3 days) and then monthly (+7 days) until normalized for age. Proposed treatment for hyperphosphatemia will involve increased fluids and restriction of phosphorus loaded foods. Proposed treatment for hypercalcemia, as reflected by a serum calcium level, is detailed in another section of this protocol.

To evaluate for feasibility, at 7 days to the next working business day after administration of the 250,000 IU administration of Vitamin D3, participants will be contacted by a member of the study team via phone to answer a 10-item questionnaire which is included as an appendix at the end of this protocol. This questionnaire is to assess feasibility of the 250,000 IU Vitamin D3.

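### Appendix A survey: item 1(iv) counts any constipation while the other six symptom items count an increase, and the NOTE does not ask for change from usual

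*Combined protocol and SAP*

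**What the plan says.** The Abstract makes a ten-question telephone survey, one week after the dose, the measure of feasibility. Section 4 (Study Procedures) repeats this: "This questionnaire is to assess feasibility of the 250,000 IU Vitamin D3".

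Appendix A opens with a NOTE. It limits the questions to the previous week and then says they "will be about how you usually feel or symptoms you otherwise usually have". The stem of question 1 ties the answers to the dose: "Over the last week, since you have taken the vitamin D3 of 250,000 IU have you". The items that follow are answered NO or YES. Most are comparative, for example "Experienced feeling an increased amount of nausea", "Experienced an increased amount of diarrhea" and "Experienced increased gas production, such as burping or passing gas". Item 1(iv) is not: "Experienced any constipation".

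The study calendar in Section 4 marks the questionnaire at Week 1 only. The design is single arm without placebo. The baseline information listed in Section 9 covers age, gender, pancreatic status and details of the daily vitamin; it lists no bowel or other gastrointestinal symptoms.

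**The concern.** When a symptom survey is given once, after treatment, in an uncontrolled study, the comparison with the child's usual state has to come from the wording of the questions. Six items supply it. Item 1(iv) does not, so a child whose constipation is long-standing and unchanged has only one truthful answer, YES. The NOTE does not repair this. Taken literally, it points the respondent towards usual symptoms when it should ask for departures from them.

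The population makes the issue practical. Section 3 (Background) says that cystic fibrosis can affect the gastrointestinal tract, so some bowel symptoms before the dose are foreseeable.

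At stake is the interpretation of one item, and the clarity of the others, in an instrument that serves a secondary objective. If the symptom answers are reported as percentages side by side, the constipation figure will be on a different scale from the rest, and a reader could take usual constipation for an effect of the dose.

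**Working it through.** **1. Reproduce the stated length.** Question 1 has 6 sub-items and questions 2 to 5 add 4, so 6 + 4 = 10. This matches the ten questions stated in the Abstract.

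**2. Classify the items.**

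| Item | Topic | What it asks |
|---|---|---|
| 1(i) | nausea | increase |
| 1(ii) | emesis | increase |
| 1(iii) | diarrhea | increase |
| 1(iv) | constipation | any occurrence |
| 1(v) | gas | increase |
| 1(vi) | abdominal pain | increase |
| 2 | heartburn or reflux | increase |
| 3, 4, 5 | ease, willingness to repeat, preference | acceptability |

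That is 7 symptom items (6 on increase, 1 on any occurrence) and 3 acceptability items.

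**3. Look for a comparator elsewhere.** There is no pre-dose administration in the study calendar, no control arm in Section 4, and no gastrointestinal symptom in the Section 9 baseline list. Sections 2 and 9 mention initial and follow-up questionnaires, but the calendar schedules only the Week 1 call, so that phrase does not supply a baseline.

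**4. Follow one child through the form.** Take a child with the same constipation before and after the dose, and no other change. Item 1(iv), as worded, gives YES. Had it used the form of item 1(iii), it would give NO. The difference comes from the wording alone.

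**5. Size, for item 1(iv) only.** Let p be the share of children with constipation in a usual week. The documents do not give p; 5% to 30% is an assumed range. The planned sample size is n = 30 (Section 9). With no dose effect, and children treated as independent:

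- expected YES answers = n × p
- chance of at least one YES = 1 − (1 − p)^n

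| Assumed p | Expected YES of 30 | Chance of at least one YES |
|---|---|---|
| 5% | 30 × 0.05 = 1.5 | 1 − 0.95^30 = 0.785 |
| 10% | 30 × 0.10 = 3 | 1 − 0.90^30 = 0.958 |
| 20% | 30 × 0.20 = 6 | 1 − 0.80^30 = 0.999 |
| 30% | 30 × 0.30 = 9 | 1 − 0.70^30 ≈ 1.000 |

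No such calculation is possible for the other six items, because the documents do not show how respondents would use the NOTE.

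**The case against.** The best defence is that six of the seven symptom items carry their own comparator. A child with unchanged symptoms answers NO to a question about an increase, whatever the NOTE says. Read together with those items, the NOTE most plausibly names the reference state against which an increase is judged, with words such as 'compared with' missing. This stands, and it limits the firm defect to item 1(iv).

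Three stronger readings are tempting, and the documents do not support them.

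- **All the symptom percentages are inflated.** A respondent told that the questions concern usual symptoms might say YES to an old symptom, say NO because nothing is unusual, or ignore the NOTE. The direction is unknown.
- **A tolerability or safety result is compromised.** The plan defines no tolerability endpoint, no symptom score and no rule attributing a YES to the dose. The questionnaire percentages in Section 9 may even mean completion rates, since the matching objective in Section 2 lists response rates beside recruitment and retention. The primary safety endpoint is serum calcium at one week.
- **Nothing else could ever separate old symptoms from new.** Adverse event assessment is a separate channel, scheduled from baseline to Week 52, and could address individual cases. The plan does not say, however, that it will record usual gastrointestinal symptoms or be linked to the survey answers.

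It is also fair to object that the counts rest on an assumed rate. The steatorrhea described in Section 3 is not evidence of constipation.

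What the defence does not remove is that the Abstract makes this survey the measure of feasibility. Its answers are therefore a study result, and the wording of item 1(iv) affects one of them.

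**Conclusion.** The point holds for item 1(iv): as worded, it records unchanged, long-standing constipation as a YES after the dose, and its percentage is not comparable with those of the other six symptom items. For those six, the NOTE adds ambiguity only, and no direction or size can be given.

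The size for item 1(iv) depends entirely on the assumed rate: about 1.5 to 9 YES answers of 30 with no dose effect, for an assumed 5% to 30%. That usual constipation will produce some YES answers is likely even at the low end of this range; how many cannot be settled from the documents.

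The consequence is small. The primary endpoint, the efficacy result, the accrual hold and the sample size do not depend on these answers. This is a minor measurement fault in a secondary-objective instrument, worth correcting because doing so is nearly free.

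**What to change.** Make two edits to Appendix A:

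1. Replace the NOTE with: *Answer about the past week only, compared with how you usually feel; answer YES only if the symptom is new or worse than usual.*
2. Replace item 1(iv) with: *Experienced an increased amount of constipation?* This puts it in the same form as the diarrhea item.

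The cost is two wording changes to a telephone script, with whatever approval a revised script needs. There are no extra calls, visits, samples or staff, and the survey stays at ten questions. If some calls have already been made with the present script, report those answers to item 1(iv) separately, as any constipation in the week after the dose.

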Appendix B Normal Calcium Values for age (JHACH Laboratory reference values)

| | Normal |
|--------------------|----------|
| 0 Year 00M 00D F | 7.5-11.3 |
| 0 Year 00M 00D M | 7.5-11.4 |
| 0 Year 00M 08D F | 8.4-11.9 |
| 0 Year 00M 08D M | 8.6-11.7 |
| 0 Year 01M 00D F | 8.0-11.1 |
| 0 Year 01M 00D M | 8.5-11.3 |
| 0 Year 03M 00D F | 7.7-11.5 |
| 0 Year 03M 00D M | 8.3-11.4 |
| 0 Year 06M 00D F | 7.8-11.1 |
| 0 Year 06M 00D M | 7.7-11.0 |
| 1 Year 00M F or M | 8.7-9.8 |
| 4 Year 00M F or M | 8.8-10.1 |
| 10 Year 00M F or M | 8.9-10.1 |
| 12 Year 00M F or M | 8.8-10.6 |
| 14 Year 00M F or M | 9.2-10.7 |
| 16 Year 00M F or M | 8.9-10.7 |
| 20 Year 00M F or M | 8.4-10.2 |

Appendix C Normal Urine Calcium:Creatinine Ratios for age (Harriet Lane Handbook Table 19-3)

| | Normal |
|------------------|--------|
| < 07 M F or M | 0.86 |
| 7-18 M F or M | 0.60 |
| 19 M -6 Y F or M | 0.42 |
| >6 Y F or M | 0.22 |
